
Primary aim: To compare mean weight loss between the *GR* and *IH* arms across 6 mos. We expect significantly greater weight loss in the *GR* compared to the *IH* arm.

Secondary aims. *To compare the GR and IH arms on the following:* 1) Mean weight loss (0-18 mos.); 2) The proportion of participants who achieve clinically significant weight loss ($\geq 5\%$ from baseline) at 18 mos.; 3) Changes in cardiovascular disease risk factors (blood pressure, total, HDL and LDL cholesterol, triglycerides, HbA1c for diabetics, waist circumference) from 0-6 and 0-18 mos.; 4) Changes in quality of life from 0-6 and 0-18 mos. We expect more favorable changes in all secondary outcomes in the GR compared with the IH arms. 5) Cost and contingent valuation analysis to compare costs between the GR and IH arms. Based on our experience with remote delivery for weight management using both group phone (DK76063) and virtual reality formats (DK94833), we expect GR to be less expensive than the IH arm.

Exploratory aims. *Initial weight loss is highly predictive of longer-term weight loss; therefore, we will examine the influence of the following variables on weight loss at 6 and 18 mos.:* behavioral session attendance, compliance with the recommendations for diet (energy intake, number of meals /shakes, servings of fruits/vegetables), PA (min of moderate-vigorous PA, min sedentary time), and self-monitoring of diet and PA, self-efficacy for dietary change and PA, dietary self-regulation, social support for diet/PA, barriers to PA, sleep, and medications.

BACKGROUND/SIGNIFICANCE

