Energy Expenditure of Remote Exercise Sessions (optional). Energy expenditure of the remote sessions will be assessed in a volunteer sample using a previously validated portable, open-circuit indirect calorimeter (Cosmed, Italy) which measures breath-by-breath ventilation, expired oxygen, and carbon dioxide. The flow turbine will be calibrated using a 3.0-L syringe. The lightweight (~1.5 kg) portable system will be attached by a harness around the waist and shoulders of the participant before each assessment. During exercise sessions, participants will breathe into a facemask that directs air into the unit housing the O₂ and CO₂ analyzers. Data will be retrieved for analysis via a serial port interface and software provided with the calorimeter, and aggregated over 20-second epochs for the calculation of 1-min averages. MET levels will be age corrected using the Schofield equation (88) as recommended by McMurray et al (89). Participants will be asked to wear wrist ActiGraphs during the assessment for comparison of physical activity levels between devices.

SAMPLE SIZE, STATISTICAL METHODS, AND POWER CALCULATION

Power/sample size. The mean 6 mo. weight loss in our completed trial in adults with MRDs, using a protocol similar to the *IH* arm in the proposed trial, i.e., eSLD and behavioral counseling delivered by monthly home visits, was 5.5 kg (58). This does not reach the 8.5 kg (~5%) average 6 mo. weight loss defined as clinically meaningful by current weight management guidelines (53). We expect 6 mo. weight loss in the *GR* arm, which includes weekly group counseling and group exercise, will reach or exceed 8.5 kg. To detect a clinically meaningful difference of 3 kg (133, 176-180) in 6 mos. weight loss between the *IH* and *GR* arms, with 80% power and a type 1 error rate of 0.05, assuming a common standard deviation of 6 kg, will require 64 participants/group. Secondarily, we will have 70% power to detect a 3 kg difference in a completer analysis with an attrition rate of 20%; however, we expect attrition will be lower based on experience (71, 78, 181), and our use of retention/incentive strategies to minimize loss to follow-up. Thus, a sample of 64/group will provide adequate power for both our primary intent-to-treat analysis with imputed missing data (power = 80%) and our secondary completer only analysis (70%).

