Analysis plans. *Primary aim* will use a 2-sample independent t-test to compare 6 mo. weight loss between the 2 intervention arms in both an intent-to-treat, and completer only analysis. Procedures for handling missing data are described below. We will examine the impact of baseline characteristics (age, sex, race/ethnicity, weight, type of MRD, wheelchair use, employment status, living situation, food shopping and preparation) on weight change using linear regression controlling for treatment. We will examine the main effects of each of these variables, as well as the potential interaction effect with treatment.

Secondary aim 1, a comparison of 18 mo. weight loss, will mirror the analysis for the primary aim. We will use a 2-sample t-test to compare weight change (0-18 mos.) between the 2 intervention arms. Mixed linear models will be used to compare weight change from 0-18 mos.

between intervention arms controlling for intervention arm and baseline weight. We anticipate greater loss to follow-up over time; however, we expect data to be missing at random. Under this assumption, mixed linear models will provide unbiased treatment comparisons. We will assume an autoregressive correlation structure of the dependent variable (weight) over time, and evaluate the potential for time-by-treatment interactions.

Secondary aim 2, a between arm comparison of the proportion of participants achieving $\geq 5\%$ weight loss (0-18 mos.) will be evaluated using a chi-square test. Participants without an 18 mo. weight will be classified as not meeting the $\geq 5\%$ weight loss goal. We will also examine the impact of baseline characteristics, as previously defined, on 18 mo. weight loss using logistic regression.

Secondary aims 3 and 4, between arm comparison of change in risk factors and quality of life (0-6 and 0-18 mos.) will be evaluated using a 2-sample t-test.

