Missing Data/ imputation. All analyses will be based on intent-to-treat principles and missing data for analyses of the primary aim will be imputed; therefore, oversampling for attrition is not needed. We will determine if the proportion of participants lost to follow-up differs by treatment. If so, we will determine if there are differences in demographic characteristics (sex, age, baseline weight, $p < 0.05$) between completers and those lost to follow-up. If missing data are related to treatment and/or these demographic characteristics, we will use model based multiple imputation; otherwise, we will use traditional multiple imputation. Statistical analysis will be completed with SAS version 9.4 or higher.

REFERENCES

2. Brault MW. Americans with Disabilities: 2010 Current Population Reports. Washington, DC: US Census Bureau; 2012. p. 40-131.

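### Secondary aims 3 and 4, and to a lesser extent 6-month weight, are compared with unadjusted t-tests on change; adding each outcome's baseline as a covariate would gain precision at almost no cost

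*Combined protocol and SAP*

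**What the plan says.** The statistical section, under Analysis plans, covers risk factors and quality of life in one sentence: "change in risk factors and quality of life (0-6 and 0-18 mos.) will be evaluated using a 2-sample t-test". The outcomes, listed under Secondary aims, are blood pressure, lipids, HbA1c (diabetics only), waist circumference and quality of life. Each is measured as a change over two periods, for example "Changes in quality of life from 0-6 and 0-18 mos". Baseline values are therefore already needed.

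Weight is handled in three places:

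- **6-month weight (primary aim):** the named comparison is a "2-sample independent t-test to compare 6 mo. weight loss between the 2 intervention arms in both an intent-to-treat, and completer only analysis". The plan also examines a list of baseline characteristics, including weight, "on weight change using linear regression controlling for treatment". The stated purpose of that regression is to study those characteristics, not to estimate the treatment effect.
- **18-month weight (secondary aim 1):** a t-test is planned, and beside it a mixed model comparing weight change "between intervention arms controlling for intervention arm and baseline weight".
- **Sample size:** the calculation is for 6-month weight only, "assuming a common standard deviation of 6 kg, will require 64 participants/group".

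The Missing Data/imputation section says that "missing data for analyses of the primary aim will be imputed". It makes no such statement for aims 3 and 4.

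**The concern.** When an outcome's baseline predicts its change, a change-score t-test leaves explainable variation in the error term. A model that includes the baseline removes it and gives a narrower interval from the same participants. The plan already does this for weight over 0-18 months, so the method is accepted; it has not been extended to aims 3 and 4.

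The protocol predicts more favorable results in the group remote arm on all secondary outcomes, so these comparisons are meant to be informative. No power is stated for them. With imputation described only for the primary aim, they may also rest on fewer participants than were randomized. At stake is precision: a real difference in a risk factor or in quality of life may be estimated too loosely to be recognized.

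**Working it through.** **Inputs from the plan.** Difference 3 kg, SD of 6-month change 6 kg, alpha 0.05 (taken as two-sided), 64 per arm, 20% attrition for completers (64 × 0.8 ≈ 51 per arm).

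**Assumed inputs, because the documents do not give them.** Pre-post correlation r = 0.4 to 0.9 for aims 3 and 4; ratio k of follow-up SD to baseline SD = 1, then 0.9 and 1.1; SD of baseline weight 20-30 kg.

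**Step 1: reproduce the plan's figures.** With the noncentral t distribution, 3/6 = 0.5 SD at 64 per arm gives 80.1% power. At 51 per arm it gives 70.6%, in line with the stated "70% power to detect a 3 kg difference in a completer analysis with an attrition rate of 20" percent. Both figures reproduce.

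**Step 2: variance ratio for aims 3 and 4.** With common variance σ², the change score has variance 2σ²(1 − r). After adjustment for baseline, the residual variance is σ²(1 − r²). The ratio is (1 − r²) / [2(1 − r)] = (1 + r)/2. Estimating the covariate multiplies this by 1 + 1/(N − 4), which is 1.0081 at N = 128 and 1.0102 at N = 102, and the error degrees of freedom are N − 3.

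| r | (1 + r)/2 | with covariate cost, N = 128 | 95% CI width ratio | power at 64 per arm (t-test 80.1%) | power at 51 per arm (t-test 70.6%) |
|---|---|---|---|---|---|
| 0.4 | 0.70 | 0.706 | 0.840 | 91.6% | 84.5% |
| 0.6 | 0.80 | 0.806 | 0.898 | 87.8% | 79.4% |
| 0.8 | 0.90 | 0.907 | 0.953 | 83.8% | 74.6% |
| 0.9 | 0.95 | 0.958 | 0.979 | 81.8% | 72.3% |

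Power is for an effect of 0.5 SD of change, the same standardized size as 3 kg over 6 kg. Simulation with 100,000 runs at 64 per arm gave 91.6%, 88.1%, 83.8% and 82.0%.

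**Step 3: unequal variances.** The ratio becomes k²(1 − r²) / (1 + k² − 2rk). At k = 0.9 it runs from 0.62 to 0.81. At k = 1.1 it runs from 0.76 at r = 0.4 to 1.00 at r = 0.9. In that last corner there is nothing to gain, and the covariate cost makes it a very slight loss.

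**Step 4: 6-month weight.** Suppose loss is proportional to starting weight, with slope b = 0.041 (the earlier trial's 4.1% loss at 6 months) to 0.05 (the 5% threshold). Then R² = (b × SD of baseline weight)² / 36.

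- b = 0.041, SD 20 kg: R² = 0.82²/36 = 0.019, power 80.6%.
- b = 0.05, SD 30 kg: R² = 1.5²/36 = 0.063, power 82.3%.

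The CI half-width falls from 2.10 kg to between 2.09 and 2.04 kg. Completer power rises from 70.6% to 70.9-72.9%. A different assumption, equal variances with a baseline SD of 15-30 kg, implies r = 0.92-0.98 and power of 81.7-80.5% before the covariate cost, which leads to the same conclusion.

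**Step 5: cost if baseline is uninformative.** With R² = 0, power at 64 per arm is 79.8% against 80.1%.

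**Step 6: HbA1c.** The number of diabetics is not stated. The factor 1 + 1/(N − 4) is 1.028 at an assumed 20 per arm and 1.0625 at 10 per arm. At 10 per arm the adjusted interval is still narrower at r = 0.8 or below. At r = 0.9 its squared width is about 2% larger (0.95 × 1.0625 = 1.009, plus the lost degree of freedom).

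**The case against.** The strongest reply is that nothing is broken. The t-test is unbiased under randomization, it reproduces the sample size, and the plan makes no promise of power for aims 3 and 4. That stands, and it makes this an improvement rather than a correction.

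The size of the gain also rests on values the documents do not supply. The 91.6% figure is the favorable end of the range; the other end is a gain of under two points, or none at all if r is 0.9 and variance grows over time. This stands too, which is why the result is given as a range.

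For 6-month weight the benefit is at most about 0.06 kg of interval half-width, and a baseline-adjusted coefficient may come out of the planned regression anyway. Replacing a primary estimate in a document dated January 2024 could look data-driven. That limits what should be done for weight, but does not touch aims 3 and 4. For 18-month weight the adjusted model is already planned, so what remains is to say which of the two analyses is the treatment estimate.

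The 51 per arm comes from the 6-month completer calculation, and the plan expects greater loss later, so it should not be read as a forecast for 18 months. HbA1c is a fair exception to describing the change as nearly free, but the possible loss there is minor.

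**Conclusion.** The point holds as a nearly free improvement. Aims 3 and 4 have only an unadjusted comparison. Under equal variances and r between 0.4 and 0.9, adding the baseline cuts the variance to about 71-96% of its present value after the cost of the covariate. The most that can be lost at full sample size is about 0.3 points of power. The gain is largest for outcomes that track weakly from baseline to follow-up and fades for those that track strongly.

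For 6-month weight the gain is real but small, roughly 0.5 to 2 points of power under the assumptions above. The planned t-tests would give valid answers; the adjusted models would usually give tighter ones.

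**What to change.** **Aims 3 and 4 (the main change).** For each outcome, at 6 and at 18 months, estimate the arm effect from a linear model of change on arm and that outcome's own baseline value. Specify this before those data are examined, or disclose the timing. For HbA1c, note that the benefit depends on how many diabetics are enrolled.

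**6-month weight.** If unblinded outcome data have not been examined, take as the treatment estimate the arm coefficient from a linear model of weight change on arm and baseline weight, fitted in each imputed data set, and keep the t-test as supportive. If the data have been seen, keep the t-test as primary and report the adjusted estimate as supportive.

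**18-month weight.** Name the baseline-adjusted mixed model already planned as the treatment estimate.

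**Cost.** SAP wording, one regression per outcome and time point in the SAS software already planned, and one degree of freedom per model. There are no new data and no change to the sample size. The one real constraint is timing for the primary analysis, because the document does not say whether outcome data have been seen.

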We propose a 2-arm randomized trial (group remote (*GR*) vs. individual home visit (*IH*)) using intent-to-treat principles, to compare body weight following weight loss (6 mos.) and maintenance (18 mos.) in overweight/obese adults with MRDs. interventions will be delivered by trained health educators and will include behavioral sessions, a reduced energy diet (eSLD), increased PA, and self-monitoring of weight using electronic scales. The *GR* arm will be delivered via video conferencing (Zoom™ software) on a tablet computer (iPad mini) with self-monitoring of diet and PA using commercially available technologies. Participants in the *IH* arm will self-monitor diet and PA using paper and pencil records. Due to COVID-19, all Cohort 1 *IH* intervention meetings will be held by phone per CDC social distancing recommendations. Participants are asked to send pictures of the tracking sheets to the health educator prior to the phone meeting. The primary outcome (weight) will be assessed during home visits at baseline (mo. 0), following weight loss (6 mos.), during (12 mos.) and at the end of maintenance (18 mos.). Our group has experience with all proposed intervention components and outcome assessments from previously completed (44, 58, 71, 78, 88, 89) or on-going trials (DK83589, HD79642). The following design attributes, described in detail subsequently, ensure the scientific rigor of the proposed trial: 1) Randomized design with equal allocation to groups, with allocation assignment concealed. 2) Adequate statistical power to address the primary aim. 3) Strategies to ensure the recruitment of sufficient participants to achieve our desired sample size. 4) Retention/incentive strategies to reduce loss to follow-up. 5) Controlling for attention by maintaining equal contact in both groups. 6) Secondary/exploratory aims to maximize the use of data, e.g., analysis to examine the impact of process variables/participant characteristics on

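### Secondary aims 3 and 4 (risk factors, quality of life) have no missing-data method, so their 0-18 month t-tests are by default completer analyses under an intent-to-treat label

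*Combined protocol and SAP*

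**What the plan says.** The Missing Data/ imputation section states: "All analyses will be based on intent-to-treat principles and missing data for analyses of the primary aim will be imputed". It gives no separate rule for secondary outcomes.

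Analysis plans then treats the aims differently:

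- **Secondary aim 1 (18-month weight)** follows the primary analysis and adds mixed linear models. The plan expects more loss over time, takes it to be missing at random, and says of weight: "Under this assumption, mixed linear models will provide unbiased treatment comparisons".
- **Secondary aim 2 (at least 5% loss at 18 months)** counts a missing 18-month weight as failure.
- **Secondary aims 3 and 4 (risk factors, quality of life)** get one sentence: the between-arm comparison of change ("0-6 and 0-18 mos.) will be evaluated using a 2-sample t-test"). No imputation, mixed model or other rule for missing values is attached.

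Aims and Hypotheses lists "Changes in cardiovascular disease risk factors (blood pressure, total, HDL and LDL cholesterol" and the remaining risk factors, and quality of life, for both 0-6 and 0-18 months. A 6-month value is therefore planned for each of these outcomes.

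**The concern.** A t-test on 0-18 month change needs an 18-month value. Someone seen at baseline and 6 months who then leaves still contributes to the mixed model for weight, but not to the 18-month tests of blood pressure, lipids, waist circumference or the SF-36E.

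Missing at random allows dropout to depend on results already observed. The t-test ignores the 6-month result, so it cannot correct for such dependence, whereas the model named for weight can. The two formats differ a good deal (remote group against individual home visit), and the plan itself intends to test whether loss differs by treatment, so unequal loss is a realistic possibility.

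At stake is the reading of the 18-month secondary comparisons, for all of which the plan predicts an advantage for the remote group arm. If poor responders leave one arm more often, that arm looks better among those who remain.

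**Working it through.** **1. The plan's own figures.** Power/sample size sets out "To detect a clinically meaningful difference of 3 kg", "with 80% power and a type 1 error rate of 0.05, assuming a common standard deviation of 6 kg, will require 64 participants/group", and "70% power to detect a 3 kg difference in a completer analysis with an attrition rate of 20"%. Allocation is equal ("Randomized design with equal allocation to groups, with allocation assignment concealed"). The standardised effect is 3/6 = 0.5 SD. With a two-sided 5% t-test (noncentral t):

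- 64 per arm gives 80.1% power.
- 64 × 0.8 = 51 per arm gives 70.6% power.

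Both stated figures reproduce. They concern 6-month weight; the documents give no SD, effect size, 18-month attrition or visit-to-visit correlation for aims 3 and 4.

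**2. How many a completer t-test leaves out.** Rates other than 20% are assumed.

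| Loss | Kept per arm | Left out of 128 | Power for 0.5 SD |
|---|---|---|---|
| 10% | 58 | 12 | 76% |
| 20% | 51 | 26 | 71% |
| 30% | 45 | 38 | 65% |
| 40% | 38 | 52 | 58% |

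**3. Bias with no true difference.** Let x and y be the standardised 6- and 18-month improvements, with correlation r. Assume logit P(dropout) = a − x, which is odds of dropout 2.7 times higher per SD of poorer 6-month change, and choose a to give the stated loss. Let m be the mean of x among those who stay. Their expected y is r × m, so the bias in the between-arm difference is r × (m₂ − m₁), in favour of the arm with the larger m.

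Numerical integration gives m = 0.091, 0.133, 0.173, 0.253 and 0.292 at 10%, 15%, 20%, 30% and 35% loss.

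| Loss in the two arms | m₂ − m₁ | Bias in SD (r = 0.4, 0.6, 0.8) |
|---|---|---|
| 20% and 20% | 0 | 0, 0, 0 |
| 15% and 20% | 0.041 | 0.02, 0.02, 0.03 |
| 10% and 20% | 0.082 | 0.03, 0.05, 0.07 |
| 15% and 30% | 0.120 | 0.05, 0.07, 0.10 |
| 10% and 35% | 0.202 | 0.08, 0.12, 0.16 |
| 20% unrelated to outcome, 30% selective | 0.253 | 0.10, 0.15, 0.20 |

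**4. Bias with a true difference of 0.5 SD.** This used 4,000 simulated trials of 64 per arm, about 20% loss after month 6, and r from 0.5 to 0.8. The completer t-test was compared with a by-arm regression estimate that uses the 6-month value, standing in for a mixed model or multiple imputation.

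| Dropout | Completer bias (SD) | Using the 6-month value |
|---|---|---|
| Unrelated to outcome | about 0 | about 0 |
| Poor responders leave, same mechanism in both arms | −0.02 to −0.04 | about 0 |
| Poor responders leave the home-visit arm only | −0.09 to −0.13 | about 0 |
| Poor responders leave one arm, good responders the other | −0.17 to −0.26 | about 0 |

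When dropout is unrelated to outcome, the standard error of the difference falls from 0.198 SD (check: √(2/51) = 0.198) to 0.185-0.193 SD once 6-month values are used, a gain of about 3-7%.

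**The case against.** The strongest reply is that the plan is silent rather than wrong, and that the harm is small under moderate conditions. Much of this stands.

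- A reader might infer that every aim except the primary is unprotected. The documents do not support that: aim 1 follows the primary analysis and adds mixed models, and aim 2 has a failure rule. The gap is confined to aims 3 and 4.
- A reader might infer that the plan orders the deletion of dropouts. It does not say so. The imputation sentence serves to explain why the sample is not inflated for attrition, and the later sentences on choosing an imputation method name no aim. Deletion is only the default result of a t-test on change with nothing else specified.
- A reader might infer that the t-test is invalid whenever data are missing at random. Missing at random permits dependence on earlier results but does not assert it. Even with dependence, equal loss under one mechanism and no true difference gives no bias in the arm contrast.
- The larger biases rest on unequal loss that the documents do not forecast. The one attrition figure, 20%, is attached to the 6-month completer analysis, with less expected. At 15% vs 30% loss the bias of 0.05-0.10 SD is at most about half the standard error: √(1/54 + 1/45) = 0.20 SD.
- People who leave before month 6 have only a baseline value, so little is recovered for the 0-6 month tests. How many later leavers will have a 6-month value is an inference, since no visit-specific attrition is given.

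What does not stand is that silence is harmless. Followed as written, these aims do not match the intent-to-treat sentence. If imputation was intended for them, the text still has to say so.

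**Conclusion.** The point holds for secondary aims 3 and 4. They carry an intent-to-treat label, have no missing-data method, and are by default completer analyses. Under the plan's own missing-at-random expectation, the 0-18 month t-test can be biased when dropout depends on the 6-month result and the arms differ in rate of loss, mechanism of loss or 6-month response.

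The illustrative size, with dropout slope, correlation and 18-month loss all assumed, runs from about 0 SD (equal loss, same mechanism, no true difference), through 0.02-0.07 SD for modest imbalance and 0.05-0.16 SD for marked imbalance, to about 0.2 SD when loss is selective in one arm only. Opposite selection in the two arms, the worst case examined, exceeds this. If loss is unrelated to outcome, the cost is a small loss of precision.

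These are secondary outcomes. The primary conclusion is unaffected, and the weight analyses already have their own handling. The change is worth making because a better method is already in the plan for weight, not because serious bias has been shown.

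**What to change.** For each outcome under aims 3 and 4, fit one mixed model to all observed baseline, 6- and 18-month values, with arm, visit and arm-by-visit terms, and take the 6- and 18-month arm contrasts from it. Alternatively, multiply impute the missing values from arm, baseline and 6-month values. Keep the 2-sample t-test as a labelled completer sensitivity analysis.

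Rewrite the Missing Data/ imputation section so that it states, aim by aim, how missing values are handled and agrees with Analysis plans. State that HbA1c is analysed in the diabetic subset only, since the same model there will rest on fewer people.

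The cost is SAP wording and modest programming on data already scheduled. The gain is mainly at 18 months. The method relies on missing at random, which the plan already accepts for weight.

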Exploratory aims will examine the influence of the following on weight loss at 6 mos.: behavioral session attendance, compliance with the recommendations for diet (energy intake, number of meals/shakes, servings of fruits/vegetables), PA (min of moderate-vigorous PA, min sedentary time), self-monitoring of diet and PA, sleep, and medications assessed over the time period of interest, i.e. (0-6 and 0-18 mos.) and the change in self-efficacy for PA and dietary change, dietary self-regulation, social support for diet/PA, and barriers to PA from 0-6 mos. We will examine the influence of these factors as covariates, in addition to treatment, on weight loss at 6 mos. As we have 128 observations with a rule of thumb of at least 30 observations for each variable in the model, judicious model selection will be completed as we can only expect to identify ~ 4 variables that are related to weight loss in a single model. First, we will assess if these variables differ by treatment at the 0.10 level and if they do they will be considered for future modeling. If in a two-factor model, the variable and treatment have a potential interaction at the 0.10 level that interaction will be considered for future modeling. Subsequently, the main effects and interaction effects along with treatment will be examined in a joint model. Given the pitfalls of forward and backward selection, we will utilize best subsets criteria based upon Mallow's Cp statistic to produce the most parsimonious and least biased model of weight loss at 6 months. This should allow us to identify what variables most highly influence our outcome along with treatment and/or the mechanism(s) of action that are impacting weight loss. We will do the same for weight loss at 18 months, as this measure may have similar or different variables that impact this long-term outcome.

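### The exploratory screen admits main effects by whether they differ between arms, not by association with weight loss, so it tends to lose predictors that are balanced across arms

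*Combined protocol and SAP*

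**What the plan says.** The exploratory aims (Aims and Hypotheses) state the goal: "we will examine the influence of the following variables on weight loss at 6 and 18 mos". The candidates include session attendance, diet and activity compliance, self-monitoring, self-efficacy, social support, barriers, sleep and medications.

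The exploratory paragraph under Analysis plans sets out the method.

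- **Size limit.** "As we have 128 observations with a rule of thumb of at least 30 observations for each variable in the model", so "we can only expect to identify ~ 4 variables that are related to weight loss in a single model".
- **Main-effect screen.** "we will assess if these variables differ by treatment at the 0.10 level and if they do they will be considered" for later modelling.
- **Interaction screen.** If in a two-factor model "the variable and treatment have a potential interaction at the 0.10 level that interaction will be considered for future modeling".
- **Selection.** What has been taken forward is examined in a joint model with treatment, and "we will utilize best subsets criteria based upon Mallow's Cp statistic".
- **Purpose.** The result should "identify what variables most highly influence our outcome along with treatment and/or the mechanism(s) of action that are impacting weight loss".

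The same procedure is to be repeated for 18-month weight loss. Under the primary aim, baseline characteristics are handled differently: weight change is regressed on them controlling for treatment, and main effects and interactions are examined with no prior screen on arm difference.

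**The concern.** The question is which variables influence weight loss, but the main-effect filter never looks at weight loss. It asks whether the variable's mean differs between the group remote (GR) and individual home visit (IH) arms. The two-factor model would estimate the variable's own effect, yet the plan uses only its interaction term.

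A strong predictor that is similar in both arms is therefore likely to be left out, and best subsets can choose only among what it is given. The design makes this more likely for some candidates. Session frequency and contact are matched between arms, session content is the same, and both arms are prescribed the same diet. The better that matching works, the more likely the related compliance variables are screened out, whatever their role in weight loss.

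At stake is the list of reported drivers of weight loss at 6 and 18 months, which would be used to refine or implement the intervention.

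**Working it through.** **Inputs from the documents.** 64 per arm (128 in total), arm difference 3 kg, SD 6 kg, screening level 0.10, at least 30 observations per variable.

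**Assumed, not in the documents.** Within-arm correlation r between a candidate and weight loss of 0.3 to 0.5 (0 for an irrelevant variable), and true standardised arm difference d in the candidate of 0 to 1.0. Tests are two-sided, because sidedness is not stated.

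**The plan's own figures.** 128/30 = 4.27, which agrees with about 4 variables. For 3 kg, SD 6 kg and 64 per arm, the noncentral t gives power of 80.1%, which agrees with the stated 80%. The plan gives no operating characteristics for the screen, so they are derived here.

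**1. Balanced predictor, main-effect route.** With d = 0 the arm-difference test is under its null hypothesis, so entry probability is 0.10 whatever the value of r. Simulation (4,000 trials per setting) gave 9.5% at r = 0.5, 9.7% at 0.4 and 10.1% at 0.3.

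**2. Adding the interaction route.** If the slope is the same in both arms, that test is also null: 1 − 0.90 × 0.90 = 0.19. Simulation gave 18% to 20%. What enters by this route is the interaction.

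**3. Predictor that differs by arm.** Noncentrality is d × √(64/2) = 5.657d, with 126 df and a critical value of 1.657.

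| d (SD) | Noncentrality | Main-effect entry |
|---|---|---|
| 0 | 0 | 10% |
| 0.2 | 1.13 | 30% |
| 0.3 | 1.70 | 52% |
| 0.4 | 2.26 | 73% |
| 0.5 | 2.83 | 88% |

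None of these figures depends on r.

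**4. Screening on weight loss instead.** For the candidate's effect adjusted for arm, tested at 0.10, noncentrality is r/√(1 − r²) × √128, with 125 df.

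| r | Noncentrality | Entry |
|---|---|---|
| 0.2 | 2.31 | 74% |
| 0.3 | 3.56 | 97% |
| 0.4 | 4.94 | over 99.9% |
| 0.5 | 6.53 | about 100% |

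An irrelevant variable enters about 10% of the time, however much it differs by arm.

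**5. Irrelevant variable that differs by arm, under the plan.** At r = 0 and d = 0.5 it passes the main-effect screen 88% of the time, and over 99% at d = 0.8. Mallows' Cp does use weight loss. In a one-variable approximation it keeps a term when t² > 2, which an irrelevant term meets about 16% of the time. Simulated probability of being both admitted and kept was 14% at d = 0.5 and 16% at d = 0.8 and 1.0.

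**6. Chance entries.** The exploratory paragraph yields about 16 candidates by my count. If all were balanced, 16 × 0.10 = 1.6 would enter as main effects by chance alone, unrelated to their predictive value.

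**The case against.** **The text does not say that other variables are dropped.** It says that those differing by arm will be considered, and an earlier sentence promises to examine the factors as covariates alongside treatment. This is fair as to wording. But no other main-effect route is given, and the screen exists to bring the list down to about 4 variables. Exclusion is the natural reading. If another is meant, the plan should state it.

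**The aim also covers mechanisms.** This stands. A mechanism of the arm effect should differ between arms, so the check is relevant to that half of the sentence. A reader might infer that the screen defeats the whole exploratory aim. The documents do not support that, because only the predictor half is poorly served.

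**Irrelevant variables do not fill the final model.** This also stands. A reader might take the 88% pass rate as the rate of false findings. The plan sends admitted variables on to Cp, which leaves about 14% to 16% of them.

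**The 10% to 19% figure is the case of no arm difference.** Correct. It should not be applied to the whole list. The GR arm has live group exercise and app-based self-monitoring, and is described as lowering barriers to attendance and activity, so some candidates may well differ. The range over d is given for that reason.

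**Selecting on the outcome brings its own optimism.** True. It is a reason to validate and label the results, but not a reason to select on something other than the outcome.

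**Conclusion.** The screen is wrong as written for the predictor question, in the exploratory aims only. Admission of a main effect depends on arm difference and never on association with weight loss, so the procedure cannot reliably name the variables that matter most. A predictor balanced across arms is left out about 81% of the time counting both routes, and 90% as a main effect. A test on weight loss adjusted for arm would miss at most about 3% of such predictors at r = 0.3 to 0.5. The loss shrinks as the true arm difference grows, and main-effect entry reaches 88% at 0.5 SD. Lost predictors are the main harm. Irrelevant variables retained are a lesser one.

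The values of r and d are assumptions, and the Cp figures rest on a one-variable approximation. The 10% rate for a balanced variable depends only on the 0.10 level.

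A reader might also infer that the treatment comparison is compromised. It is not. The primary and secondary analyses, and the unscreened regressions on baseline characteristics, do not use this screen.

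**What to change.** For the predictor question, remove the arm-difference gate. Select on association with weight loss in a model with treatment forced in, as the plan already does for baseline characteristics. Two ways would serve: carry forward main effects reaching 0.10 in the model with treatment, or enter all candidates into best subsets or a penalised regression. Either should stay within the limit of about 4 variables. The choice should be stated in advance and used for both the 6- and 18-month models.

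Keep the arm-difference test only as the first step of a separate mediation analysis for mechanisms of action.

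The cost is a few sentences in the analysis plan, with no new data, visits or participants. The price is a wider search with some selection optimism. The results should therefore be labelled hypothesis-generating and reported with a bootstrap or cross-validation check.
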